# **1.2 Schedule of Activities**

The schedule of activities table provides an overview of the subject visits and study procedures. The investigator may schedule visits (unplanned visits) in addition to those listed on the schedule of activities, to conduct evaluations or assessments required to protect the well-being of the subject.

	Screening		Study Visits			
Procedure/Assessment	Visit 1		Visit 2 Baseline (Day 1)	Visit 3 Week 6 (Day 43±4)	Visit 4 Week 12 (Day 85±4)	
Informed consent 	X					
Demographics	X					
Confirm WeChat application available on subject's mobile phone 	X					
DH screening questionnaire	Х					
Confirm absence of anti-sensitivity ingredients & DH claims from subject's own oral care products	X					
Review subject's normal oral hygiene routine, specifically their rinsing habits	X					
Medical history and prior/current medication/treatment review	X					
Changes in health and medications/treatments		Accl	X	X	X	

 
Compliance checks
 
Check returned study supplies, review diary & evaluate compliance with twice daily use.
 
Check compliance with Lifestyle Guidelines/ Medication requirements.
 
		Acclimatization Period (14-28 Days)	X	X	x	
Check brushing videos to confirm compliance with acclimatisation toothpaste usage instructions		iod (14	X			
Oral soft tissue (OST) examination	Х	-28	X	X	X	
Oral hard tissue (OHT) examination	Х	Day			X	
Eligible teeth assessments (dentition exclusions, Erosion/Abrasion/Recession [EAR], Modified Gingival Index [MGI], clinical mobility)	Х	(S)				
Qualifying tactile sensitivity assessment (tactile threshold (g)) for all eligible teeth 	Х		X			
Qualifying evaporative (air) sensitivity assessments (Schiff sensitivity score, VAS) for all eligible teeth with a tactile threshold $\leq 20g^{3,4}$	X		X			

 
Identify all eligible teeth which qualify for Baseline sensitivity assessments:
 
No dentition exclusions
 
Presence of EAR
 
MGI = 0 adjacent to the test area only
 
Clinical mobility = 0
 
Tactile threshold ≤ 20g
 
Schiff sensitivity score ≥ 2
 
	х					

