- An acclimatisation period (2-4 weeks) will precede the Baseline visits. During this period, study subjects will brush twice daily with the regular fluoride toothpaste and toothbrush provided (in place of their normal oral hygiene products) and record each timed brushing occasion in a diary. The acclimatisation period will also help standardise oral hygiene practice across the study population prior to treatment.
- Subjects will complete a Screening Questionnaire (Appendix 15.2) at Visit 1; those who report experiencing DH symptoms only 'several times a month', 'once a month' or 'less than once a month' will be excluded from the study.
- Each selected test tooth must have the same qualifying Schiff sensitivity score at the Screening and Baseline visits (i.e., Schiff sensitivity score = 2 at Screening and Baseline, or Schiff sensitivity score = 3 at Screening and Baseline).

On completion of the Baseline assessments, the clinical examiner will select two test teeth from those that qualified at Screening (Visit 1) and Baseline (Visit 2) for assessment of tactile and evaporative (air) sensitivity at all subsequent visits (Table 4-1). The selection of two 'test teeth' to evaluate changes in DH is common practice in sensitivity studies (Schiff, 1994). Qualifying subjects will be stratified according to the maximum Schiff sensitivity score of their two selected test teeth to ensure treatment groups are balanced for DH severity.

DH is an episodic condition; symptoms are known to vary spontaneously (West, 2008, West et al., 2013). Baseline clinical values that would support enrolment may represent random highs

Property of GSK Consumer Healthcare - Confidential

May not be used, divulged, published or otherwise disclosed without the consent of GSKCH

Clinical Protocol Template v9.0

Page **19** of **73** 

that could be followed by regression to the mean, leaving the subject or selected test tooth without the condition under investigation during the treatment period. To help minimise the potential for this to occur on the current study, randomised subjects will be required to demonstrate consistency in DH response at both the Screening and Baseline visits.

- Randomised subjects must have a minimum of two eligible teeth (no dentition exclusions, presence of EAR, MGI = 0 adjacent to the test area only, clinical mobility = 0) with a tactile threshold ≤ 20 g and a Schiff sensitivity score ≥ 2 at both Screening and Baseline.

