#### 8.2.1.4 Clinical Examinations and Assessments

Prior to commencing the clinical examinations and assessments, subjects will be reminded how to complete a VAS (Section 9.1.3).

The following clinical examinations will be completed as described in Study Assessments and the findings recorded in the eCRF. To facilitate subject flow, source documents can be used to record the DH assessments for later transcription into the eCRF (transcription from source documents must be completed within 5 days of recording the data for each subject).

- OST examination
- Clinical assessment of tactile sensitivity (tactile threshold (g)) for each *eligible tooth identified at Screening* (eligibility criteria described in Section 8.1.8 and Table 4-1).
- Clinical assessment of evaporative (air) sensitivity (Schiff sensitivity score [examiner assessed], followed by VAS [subject completed]) for each eligible tooth identified at Screening with a Baseline tactile threshold of ≤ 20g.

There should be at least a 5-minute break between completing the tactile assessments and starting the evaporative (air) assessments.

Subjects must have at least two eligible teeth with the qualifying tactile threshold  $\leq 20$  g and qualifying Schiff sensitivity score  $\geq 2$  at both Screening and Baseline, and VAS  $\geq 40$  mm at Baseline to continue.

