## 9.3.1 Oral Soft Tissue (OST) Examination

The OST examination will be accomplished by direct observation and palpation, using retraction aids as appropriate, and will include examination of the labial mucosa (including lips), buccal mucosa, mucogingival folds, gingival mucosa, hard palate, soft palate, tonsillar area, pharyngeal area, tongue, sublingual area, submandibular area and salivary glands. The results of the examination will be recorded in the eCRF as either 'normal' or 'abnormal'; details of any abnormalities will be documented in the eCRF.

Any observation that changes from 'normal' to 'abnormal', or worsens, from the OST examination completed at Screening will be recorded as an AE.

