## 9.3.2 Oral Hard Tissue (OHT) Examination

CCI

The OHT examination will be accomplished by direct observation, using retraction aids as appropriate, and will identify enamel irregularities, tooth fractures, grossly carious lesions/gross decay, defective/faulty restorations (all direct & indirect restorations including fixed/removal prostheses), non-carious tooth surface loss (abrasion, attrition, abfraction and erosion), any other hard tissue irregularities (e.g., hypo/hypermineralisation, decalcification) and significant tooth staining. Observations will be listed as 'absent' or 'present'; conditions noted as 'present' will be described in the eCRF. Any observation that changes from 'absent' to 'present', or worsens, from the OHT examination completed at Screening will be recorded as an AE.

Property of GSK Consumer Healthcare - Confidential

May not be used, divulged, published or otherwise disclosed without the consent of GSKCH

Clinical Protocol Template v9.0

Page **48** of **73** 

The presence of any implants, fixed or removable dentures, fixed or removable orthodontic braces/bands, fixed orthodontic retainers, full crowns or veneers will be recorded, along with evidence of gross intra-oral neglect or the need for extensive dental therapy.

The OHT examination is also used to assess the dentition against the general and specific dentition exclusions described in Section 5.3 (Exclusion Criteria 25, 26, 27, 28 and 29 a) to f)).

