## **10.1** Definition of an Adverse Event (AE)

An AE is any untoward medical occurrence in a clinical study subject, temporally associated with the use of a study product including any washout or lead-in product (or medical device), whether or not considered related to the study product, including any washout or lead-in product (or medical device).

NOTE: An AE can therefore be any unfavorable and unintended sign (including an abnormal laboratory finding), symptom, or disease (new or exacerbated) temporally associated with the use of a study product including any washout or lead-in product (or medical device).

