# 10.3 Time Period and Frequency for Collecting AE and SAE Information

All AEs, and therefore all SAEs, will be collected immediately after a subject provides consent to participate in the study by the completion (signature) of the ICF and until 5 days following last administration of the study product (or last study procedure).

Medical occurrences that began before obtaining informed consent will be recorded in the Medical History/Current Medical Conditions section of the eCRF, not the AE section.

Details recorded by the subject on a diary or similar document that meet the definition of an AE must also be discussed with the subjects and transcribed in the AE section of the eCRF.

All SAEs will be recorded and reported to the sponsor or designee immediately and under no circumstance should this exceed 24 hours. The investigator will submit any updated SAE data to the sponsor within 24 hours of it being available.

Investigators are not obligated to actively seek AEs or SAEs after the conclusion of the study participation. However, if the investigator learns of any SAE, including a death, at any time after a subject has been discharged from the study, and they consider the event to be reasonably related to the study product or study participation, the investigator must promptly notify the sponsor.

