#### 4.5.1 Adverse Events and Serious Adverse Events

All AEs will be reviewed by the Clinical Research Scientist or Designee prior to database lock and unblinding, and will be coded to a system organ class (SOC) and preferred term (PT) using the Medical Dictionary for Regulatory Activities (MedDRA).

AEs will be classified as oral and non-oral on the AE page of eCRF.

Treatment emergent adverse events (TEAEs) are defined as new AEs that occur on or after the first study product use at Baseline (Visit 2; if this date is missing, a suitable alternative will be used, e.g., date of randomization). AEs with an onset date/time prior to the first study product usage will be considered as non-treatment emergent. In case of misallocation, compared to the randomization schedule, TEAEs will be associated with the most recent study product received.

The following summary tables and listings will be presented by study product group.

- Table of TEAEs by SOC and PT (Table 14.3.1.1).
- Table of TEAEs by Oral/Non-Oral and PT (Table 14.3.1.2)
- Table of treatment related TEAEs by SOC and PT (Table 14.3.1.3)
- Table of treatment related TEAEs by Oral/Non-Oral and PT (Table 14.3.1.4)
- Table of AEs related to COVID-19 by SOC and PT (Table 14.3.1.5).
- Listing of all AEs (Listing 16.2.7.1 for all randomized subjects; Listing 16.2.7.2 for non-randomized subjects)
- Listing of all AEs related to COVID-19 subject (Listing 16.2.7.3 for all screened subjects)
- Listing of deaths (Listing 14.3.2.1)
- Listing of non-fatal SAEs (Listing 14.3.2.2)
- Listing of TEAEs leading to study or product discontinuation (Listing 14.3.2.3)
- Listing of TEAEs classified as Oral (Listing 14.3.2.4)

In the event that there is nothing to report, a null table or listing will be produced.

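### Soft-tissue findings on study product are compared with Screening only, so a finding that cleared by Baseline and then returned may not be recorded as a TEAE

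*Protocol*

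**What the plan says.** The rule in Protocol 9.3.1, repeated word for word in SAP 4.5.2.1, is: "Any observation that changes from 'normal' to 'abnormal', or worsens, from the OST examination completed at Screening will be recorded as an AE". It names one reference visit, Screening, for all later examinations.

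The schedule row "Oral soft tissue (OST) examination" (Protocol 1.2) is marked at all four visits. Protocol 8.2.1.4 lists "OST examination" among the Visit 2 procedures, ahead of the first supervised brushing with study toothpaste in 8.2.1.8. Between the two visits lies the run-in: "An acclimatisation period (2-4 weeks) will precede the Baseline visits" (Protocol 4.2).

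Treatment emergence is settled separately, by onset. SAP 4.5.1 counts new AEs from first study product use at Visit 2 and adds: "AEs with an onset date/time prior to the first study product usage will be considered as non-treatment emergent". (Protocol 12.3.3 has the same starting point but labels Baseline as Visit 1; the schedule and the SAP place it at Visit 2.) SAP 3.1 sets Baseline at the Visit 2 pre-brushing assessment for every endpoint. TEAEs are the only safety endpoint.

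AE collection starts earlier than treatment emergence: "All AEs, and therefore all SAEs, will be collected immediately after a subject provides consent to participate in the study" (Protocol 10.3). The AE definition in 10.1 covers events "temporally associated with the use of a study product including any washout or lead-in product". SAP Table 14.3.4.1 counts subjects with and without abnormalities by visit and product, and two listings give the individual OST results.

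**The concern.** The safety objective is oral tolerability of the study toothpastes over 12 weeks. Findings that an examiner sees in the mouth are the events most directly relevant to it. The endpoint is counted from first use at Visit 2, but the rule that feeds examiner findings into it looks back past Visit 2 to a state that existed before the run-in. Where a subject's state changed between Screening and Baseline, the two reference points can disagree about whether something happened on study product.

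The disagreement matters in one direction. Suppose a site is abnormal at Screening, normal at the Visit 2 examination, and abnormal to the same degree at Week 6. Relative to the start of treatment this is a new finding. Relative to Screening it is neither a change from normal nor a worsening, so the rule is silent. The examination that would show the change has already been done and recorded.

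**Working it through.** The plan states no figure on this point, so there is none to reproduce. The check has three parts.

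**1. Which sequences does the Screening reference miss?** Write each sequence as (Screening, Baseline, later visit). The plan's rule flags a sequence when later > Screening. A Baseline-referenced rule flags it when later > Baseline.

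- Two states (0 normal, 1 abnormal) give 8 sequences. Two worsen after Baseline: (0,0,1) and (1,0,1). The plan's rule flags (0,0,1) and misses (1,0,1).
- The rule also covers worsening, so I repeated this with three grades. The grades are my assumption; the documents define none. Of 27 sequences, 9 worsen after Baseline. The plan's rule flags 5: (0,0,1), (0,0,2), (0,1,2), (1,0,2), (1,1,2). It misses 4: (1,0,1), (2,0,1), (2,0,2), (2,1,2). In all 4 the finding was present at Screening, had resolved or improved by Baseline, and came back to no worse than its Screening level.

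These are counts of patterns, not of patients.

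**2. Do other AE provisions catch the missed pattern?** Set Protocol 10.1 and 10.4 beside it:

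- The exacerbation clause in 10.1 turns on a rise in frequency or intensity. A return at the Screening level is not more intense, and whether it counts as more frequent is open.
- The clause on new conditions detected after study product administration does not clearly apply, because this finding was already detected at Screening.
- The exclusions in 10.1 remove expected fluctuations of conditions present at study start that do not worsen. An investigator could read the recurrence as exactly that.
- Section 10.4 requires directly observed AEs to be reported, but presupposes that the finding is an AE.

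So the pattern is neither clearly in nor clearly out.

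**3. How many subjects?** The documents give no OST rates, so every rate here is assumed. Number not flagged = N × a × r × w, where N = 240 (planned randomised, all arms), a = abnormal at Screening, r = share resolved by Baseline, w = share returning on product.

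- a = 2%, r = 50%, w = 5%: 240 × 0.02 × 0.50 × 0.05 = 0.12.
- a = 8%, r = 50%, w = 30%: 240 × 0.08 × 0.50 × 0.30 = 2.88.
- Wider limits: 240 × 0.02 × 0.25 × 0.05 = 0.06, and 240 × 0.20 × 0.75 × 0.30 = 10.8. The upper limit needs all three rates at their extremes.

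All of these are counts before any other AE route is applied.

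**4. Does the proposed fix lose anything?** A Baseline reference alone would not flag (0,1,1), (0,2,1), (0,2,2) or (1,2,2) at the later visit, all of which the Screening rule does flag. In each of the four, Baseline is worse than Screening, so comparing Baseline with Screening flags them at Visit 2. Using both comparisons catches all 9 post-Baseline worsenings and keeps the run-in onsets.

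**The case against.** The Screening reference has a purpose. AEs are collected from consent and include those on the lead-in product, so a pre-run-in reference is needed to capture run-in lesions. This stands, and it is why Screening should be kept as a reference and not replaced.

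The rule says what must be recorded; it does not say that other findings are not AEs. Direct observation, non-leading questions and diary review at each visit, and the general AE definition may still bring the recurrence in. That is fair, and it limits the conclusion to *may not be recorded*. It does not close the gap, because the fluctuation exclusion points the other way and nothing tells the examiner which prevails.

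The data are not lost: the listings show a subject's full sequence. This is also true. But Table 14.3.4.1 gives only visit totals, in which one subject's clearing can offset another's new finding, and no display summarises within-subject change from Baseline by product.

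The population makes Screening abnormalities uncommon, since inclusion criterion 4 requires good oral health without clinically significant or relevant abnormality on oral examination. That supports a small number, though minor findings can remain.

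Two stronger readings are tempting, and the documents do not support them. A reader might infer that run-in lesions are credited to the study product. They are not: such a lesion is already worse than Screening at the Visit 2 examination, is recorded then with an onset before first use, and is non-treatment emergent under SAP 4.5.1. A reader might also extend the point to hard tissue, where the rule likewise measures change "from the OHT examination completed at Screening will be recorded as an AE". No hard-tissue examination is scheduled at Baseline, so there is no unused reference there and the argument does not carry over.

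**Conclusion.** The point holds in a narrow form. The OST rule and the TEAE endpoint use different starting points, and one pattern falls between them: present at Screening, resolved or improved at Baseline, back on study product at no worse than the Screening level. Such a finding does not trigger the OST rule, and Protocol 10.1 leaves open whether it must be recorded, so it may be missing from the TEAE tables.

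A reader might infer that treatment-emergent oral lesions in general go unrecorded. They do not: a lesion absent at both Screening and Baseline, or one that becomes worse than at Screening, is flagged by the current rule.

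The size is probably small: about 0.1 to 2.9 subjects of 240 under the narrower assumed rates, 0.06 to 10.8 under the wider ones, before other AE routes. No rate comes from the documents. The primary analysis and the success criterion are unaffected. This is an improvement worth making because it is nearly free, not a defect that threatens the trial.

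**What to change.** In Protocol 9.3.1 and SAP 4.5.2.1:

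- Keep the comparison of the Baseline OST with Screening, so that run-in lesions continue to be recorded as AEs from consent onward.
- Add that Week 6 and Week 12 OST findings are also compared with the Visit 2 pre-brushing OST, and that any change from normal to abnormal, or any worsening, against Baseline is recorded as an AE.

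In SAP Table 14.3.4.1, add the shift from Baseline at Week 6 and Week 12 by study product.

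The cost is one sentence in each document, a matching eCRF instruction and a shift display from data already collected. No examination, visit or subject is added.

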## 9.3.2 Oral Hard Tissue (OHT) Examination

CCI

The OHT examination will be accomplished by direct observation, using retraction aids as appropriate, and will identify enamel irregularities, tooth fractures, grossly carious lesions/gross decay, defective/faulty restorations (all direct & indirect restorations including fixed/removal prostheses), non-carious tooth surface loss (abrasion, attrition, abfraction and erosion), any other hard tissue irregularities (e.g., hypo/hypermineralisation, decalcification) and significant tooth staining. Observations will be listed as 'absent' or 'present'; conditions noted as 'present' will be described in the eCRF. Any observation that changes from 'absent' to 'present', or worsens, from the OHT examination completed at Screening will be recorded as an AE.

Property of GSK Consumer Healthcare - Confidential

May not be used, divulged, published or otherwise disclosed without the consent of GSKCH

Clinical Protocol Template v9.0

Page **48** of **73** 

The presence of any implants, fixed or removable dentures, fixed or removable orthodontic braces/bands, fixed orthodontic retainers, full crowns or veneers will be recorded, along with evidence of gross intra-oral neglect or the need for extensive dental therapy.

The OHT examination is also used to assess the dentition against the general and specific dentition exclusions described in Section 5.3 (Exclusion Criteria 25, 26, 27, 28 and 29 a) to f)).

## 9.3.3 Pregnancy

This clinical study will evaluate toothpastes classified as general goods in China. Sponsor studies in which no drug is utilized do not require pregnancy testing.

Female subjects will provide verbal confirmation of pregnancy status at Screening (Visit 1) and will be asked to inform study staff immediately should this change at any point during the study.

Female subjects who are pregnant or intending to become pregnant during the study (self-reported) will be excluded.

# 10 ADVERSE EVENT AND SERIOUS ADVERSE EVENTS

The investigator and any qualified designees are responsible for detecting, documenting, and reporting events that meet the definition of an AE or SAE and remain responsible for following up AEs that are serious, considered related to the study product or the study, or that caused the subject to discontinue the study product or study.

## **10.1** Definition of an Adverse Event (AE)

An AE is any untoward medical occurrence in a clinical study subject, temporally associated with the use of a study product including any washout or lead-in product (or medical device), whether or not considered related to the study product, including any washout or lead-in product (or medical device).

NOTE: An AE can therefore be any unfavorable and unintended sign (including an abnormal laboratory finding), symptom, or disease (new or exacerbated) temporally associated with the use of a study product including any washout or lead-in product (or medical device).

#### Events Meeting the AE Definition:

CCI

- Any abnormal laboratory test results (hematology, clinical chemistry, or urinalysis) or other safety assessments (e.g., electrocardiogram (ECG), radiological scans, vital sign measurements), including those that worsen from baseline, considered clinically significant in the medical and scientific judgment of the investigator (i.e., not related to progression of underlying disease).
- Exacerbation of a chronic or intermittent pre-existing condition including either an increase in frequency and/or intensity of the condition.
- New conditions detected or diagnosed after study product administration even though it may have been present before the start of the study.
- Signs, symptoms, or the clinical sequelae of a suspected drug-drug interaction.
- Signs, symptoms, or the clinical sequelae of a suspected overdose of either study product or a concomitant medication. Overdose per se will not be reported as an AE/SAE unless it is an intentional overdose taken with possible suicidal/self-harming intent. Such overdoses should be reported regardless of sequelae.

Property of GSK Consumer Healthcare - Confidential

May not be used, divulged, published or otherwise disclosed without the consent of GSKCH

Clinical Protocol Template v9.0

Page **49** of **73** 

• 'Lack of efficacy' or 'failure of expected pharmacological action' per se will not be reported as an AE. Such instances will be captured in the efficacy assessments. However, the signs, symptoms, and/or clinical sequelae resulting from lack of efficacy will be reported as AE if they fulfill the definition of an AE.

